3.2.1 Sacroiliac Forward Flexion Test (SIFFT)

Everyone of the “idiopathic” low back pain participants is asked to stand, with their belt undone, leaning on one of the office counters with their legs vertical and their body, flexed at the hips, horizontal (Figure 1). This causes the innominate bones to be tilted forward with the horizontal body and lifted-up by the vertical legs while the weight of the torso brings down the spine and the sacrum. In this position, the PSISs (posterior superior iliac spines) face the examiner and are easier to palpate. The examiners then run their hands down the iliac crests to

Figure

locate the PSISs. Once these are located, they press down below the PSISs with the ulnar side of their thumbs abutting against the PSISs. They then ask the participants whether and on which side they feel pain. The pain may be due to pressure on the overstrained long dorsal sacroiliac ligaments which stabilize this joint. This is called the sacroiliac forward flexion test (SIFFT).

1: sacroiliac forward flexion test (SIFFT)

- Using a surgical marker, the examiner marks the area between his/her thumb and the PSIS on each side and writes the letter B (for before) on the painful side, on both sides if they have pain on both sides. He/she then asks the participant to stand and places a horizontal level on the lowest mark (Figure 2). He/she then measures the distance between the level and the highest mark in centimetres (Figure 3).

Figure 2: using a level on the lowest PSIS

[figure not shown]
[figure not shown]

Figure 3: measuring the distance between levels

The marks indicate the direction and extent of the malrotation:

- if the PSIS on the painful side is higher than that on the asymptomatic side, there is an anterior malrotation of the painful side ileum on the sacrum.
- If it is lower, there is a posterior malrotation of the painful side ileum on the sacrum.

The physician will record the degree of malalignment and its direction. If the participant is part of group 3 they are given a return appointment to be treated with both the exercises and the pelvic support belt one month later.

3.2.2 Corrective Exercises

- Participants assigned to Group 1 will be treated to correct the malrotation depending on whether the ileum is anteriorly or posteriorly malrotated on the sacrum.
- **In order to correct an anterior malrotation of the ilium on the sacrum**, the participants are asked to face a chair and place the foot on the affected side on the chair. They bend the knee on the unaffected side to lean it on the front of the chair, helping to stabilize the unaffected joint. Each hand then grabs the side of the chair and they lean back to force the thigh on the affected side against the ASIS. They then pull up hard to push the thigh against the ASIS, rotating it posteriorly (Figure 4).

They must hold this position without pausing for 2 minutes. This exercise is tiring and a 2-minute timer is used to ensure they hold the position for that amount of time. It is also advisable to also speak to them continuously in order to distract them while they are performing the exercise. The exercise and the reason for it is explained in the following YouTube video:

www.youtube.com/watch?v=NXNS6PNKRPo

Figure 4: correcting an anterior malrotation of the ileum on the sacrum If there is an anterior or a posterior malrotation of the affected ileum on the sacrum, if the participant is unable to perform the first corrective exercise or if the posterior sacroiliac ligaments under both the PSISs are tender, a different corrective exercise is used. This exercise requires help from someone else: in dorsal decubitus, with the knee on their anteriorly rotated side bent against their chest and their foot on the examiner's sternum, the examiner leans forward to push the thigh on the anteriorly rotated side against the ASIS. At the same time they lean on the extended thigh corresponding to the posteriorly rotated ilium on the sacrum just above the knee. This uses the sartorius which is attached to the ASIS and the rectus femoris which is attached to the AIIIS to pull the affected ilium anteriorly. When correcting an anterior sprain, lean forward forcibly, and simply stabilize the extended opposite thigh. When correcting a posterior sprain, stabilize the flexed thigh and lean heavily on the extended thigh (Figure 5). For bilateral sprains, one anterior and one posterior, force needs to be used bilaterally. Again, the position is held for 2 minutes.

anteriorly rotated side bent against their chest and their foot on the examiner's sternum, the examiner leans forward to push the thigh on the anteriorly rotated side against the ASIS. At the same time they lean on the extended thigh corresponding to the posteriorly rotated ilium on the sacrum just above the knee. This uses the sartorius which is attached to the ASIS and the rectus femoris which is attached to the AIIIS to pull the affected ilium anteriorly. When correcting an anterior sprain, lean forward forcibly, and simply stabilize the extended opposite thigh. When correcting a posterior sprain, stabilize the flexed thigh and lean heavily on the extended thigh (Figure 5). For bilateral sprains, one anterior and one posterior, force needs to be used bilaterally. Again, the position is held for 2 minutes.

Figure 5: Correcting a posterior malrotation of the affected ileum on the sacrum or a right anterior, left posterior malrotation

For those who have no one to help them, I ask them to genuflect and lean forward against their thigh on the anterior malrotated side with their hands on other side of their foot, while extending the posteriorly malrotated leg with their knee on the floor on a cushion, and, once again, to hold this position for 2 minutes. (Figure 6)

Figure 6: self correction of an anterior right, posterior left malrotation of the ileum on the sacrum.

Following the exercise, the sacroiliac joints are once again examined and the level of the PSISs is marked with the letter A for after. (Figure 7)

Figure 7: levels of the PSISs, before and after correction.

- The participants are then asked if they are still experiencing pain or tenderness to palpation in their back. Usually, if they are still symptomatic the PSISs are not entirely level. If this is the case, the pelvis is re-examined and the corrective exercise is repeated for a further 2 minutes.
- Those who accompany the patient are instructed on how to examine the PSISs to find their level and how to correct an anterior or a posterior sprain. Participants are sent home with instructions to do the exercises whenever their back pain recurs and to come back as needed.
- If the participants are unaccompanied, they are taught how to palpate their PSISs and to locate them in a full-length mirror. If they are unable to do this, they will be taught to locate their ASISs and check for their level in a full-length mirror, with the lower ASIS indicating an anterior sprain and the higher ASIS indicating a posterior sprain.
- This being done, they will be sent home for one month with instructions to repeat the SIFFT test and use the appropriate corrective exercises whenever their back pain recurs.

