In 2018 I did a chart review of 180 cases of low back pain in which I tested those who did not have lumbar pain using the SIFFT^x. I treated them with the appropriate exercise depending on the direction of the sacroiliac rotation. From this review, I found 16 cases of pain coming from the lumbar spine (9%). Of the remaining 164 given the appropriate 2 minute exercises, 78% found pain relief of which two thirds left the office entirely pain free. At that time, I also prescribed a pelvic support belt as, generally, a malrotated pelvis is an unstable pelvis^{xi}. As soon as the pelvis becomes malrotated again, the pain recurs. As the corrective exercise and pelvic support belt are two different treatments, the current research project will study them first separately for one month, then on follow-up after they have been used together for one month.

The aim of this study is to determine whether the pain relief and improved back function is temporary or if it can be reproduced and sustained by the patient at home, as needed with these two treatments. In order to test the effectiveness of each treatment alone and when they are combined, two sub-studies will be carried out as follows:

The first study is a superiority trial with a delayed control.

Population: ambulatory people between the ages of 19 and 90 suffering from low back pain, not of lumbar spine or hip origin, for at least three months.

Intervention 1 : teaching participants how to detect pelvic malrotation using the SIFFT then prescribing a two-minute exercise to correct pelvic malrotation, depending on its direction.

Intervention 2: prescribing a pelvic support belt to stabilize the pelvis.

Control: waiting list for one month, using usual treatments such as medications, alcohol and other drugs, chiropractic and other manipulation and physical therapy.

Outcome: a clinically significant change in Brief Pain Inventory (BPI) NRS pain score or in Oswestry disability Index (ODI) for low back pain.

Time: outcomes measured at baseline and after one month of using the assigned treatment at home.

The second study is a one month follow-up of the combined treatments.

Population: all previous study participants

Intervention: teaching all participants how to detect pelvic malrotation using the SIFFT then a two-minute exercise to correct pelvic malrotation depending on its direction followed by prescription of a pelvic support belt.

Control: BPI NRS pain severity score and ODI at one month assessment

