2.3 Inclusion Criteria

- Age 19 to 90 Participants present with pain in their low back (below the waist) or their buttock.
- Able to attend all 3 study visits at the participating physician’s office (assessment visit, exercise and pelvic belt visit and one- month follow-up visit)
- Able to attend the first two visits with someone willing to assist them in assessing their back and help them with the necessary exercise if need be.
- Willing to perform the corrective exercise at home as needed
- Their PSISs are not level on initial examination.

- The long dorsal sacroiliac ligament below at least one of the PSISs is tender to palpation on initial examination.

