3.2.3 Fitting for a pelvic support belt

- A pelvic support belt is a device capable of stabilizing their pelvis^{xvi}, ^{xvii}. The fact that the sacroiliac joint is malrotated indicates a laxity of the ligaments holding this joint in place. This laxity can be the result of old age, a strain, sprain, tear, the presence of relaxin in pregnancy or defective collagen as occurs in Ehlers Danlos syndrome, Marfan's syndrome and hypermobility syndrome. The sacroiliac joint would not be displaced if the ligaments stabilizing it were functioning properly^x. Unless a pelvic belt is worn, particularly during activities where the sacroiliac joints are stressed, there is a very high likelihood of a recurring malrotation. As the goal of this treatment is to provide sufferers with long-term solution for their unstable pelvis, the pelvic belt is a necessary adjunct.

- Participants assigned to group 2 will be fitted for a pelvic support belt and instructed on how to use it: the belt has to be positioned at the level of the sacrum in the back, immediately below the ASISs in front and just above the greater trochanters on the side. It has to be fitted tight, but not excessively^{xvi}, in order to ensure pelvic stability. Preferably it should be worn on top of an undershirt or a crotchless underpant to avoid skin irritation. This being done, they will be sent home for one month with instructions to use the pelvic support belt as needed, whenever they are performing activities which would normally precipitate more back pain.

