3.5 Withdrawal Procedure, Dropouts

- Participants with uneven sacroiliac joints who do not experience any relief after doing the correction exercises and/or trying out the pelvic support belt will probably not want to continue to try these exercises or wear the pelvic support belt at home.
- They will, however, be asked to try the exercise and belt at home and return in 1 month to be retested and fill out the questionnaires. At that time, all the procedures associated with the first treatment visit will be repeated.
- For those who decide to withdraw from the study, every effort will be made to contact them and ask them the questionnaire relevant to the time they withdrew,
- unless, at the time they withdraw they notify us that they do not want to answer any more questionnaires, in which case the last data collected will be entered in the database.

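### Section 3.2.2 invites the exercise arm back to the clinic as needed before month 1; the belt and waiting-list arms get no such offer, and no form item is designed to log such visits

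*Combined protocol and SAP*

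**What the plan says.** The scope of section 3.2.2 is set by its first bullet: "Participants assigned to Group 1 will be treated to correct the malrotation". After the supervised exercise at the first treatment visit, a bullet that begins with the people accompanying the patient ends: "Participants are sent home with instructions to do the exercises whenever their back pain recurs and to come back as needed". The next bullet deals with unaccompanied participants. The section then closes by saying that "they will be sent home for one month with instructions to repeat the SIFFT test" and to use the matching exercise when pain recurs, with no mention of returning early.

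The other two arms read differently. For group 2, section 3.2.3 says "they will be sent home for one month with instructions to use the pelvic support belt as needed"; there the need-based wording governs belt use, not visits. For group 3, section 3.2.1 says "they are given a return appointment to be treated with both the exercises and the pelvic support belt one month later".

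Elsewhere the plan foresees only scheduled visits. Eligibility in section 2.3 includes "Able to attend all 3 study visits". Section 4.2.1 dates the questionnaires to the first treatment visit and the one- and two-month visits. Under section 3.5, participants who get no relief will "be asked to try the exercise and belt at home and return in 1 month to be retested and fill out the questionnaires".

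Section 1.1 gives the timing for the first study: "outcomes measured at baseline and after one month of using the assigned treatment at home".

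**The concern.** The first study is meant to separate what a patient can sustain alone from the short-lived relief already seen in the office (sections 1.1 and 1.2). An open return offer to the exercise arm can bring the office component back in before the primary ODI comparison at month 1.

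The plan itself gives reasons to expect some returns. Section 3.2.3 considers recurrence very likely without a belt, and group 1 has no belt until month 1. Section 1.1 says pain comes back once the pelvis malrotates again. One of the exercises in section 3.2.2 needs a second person to apply force.

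The measures could register a late visit. The BPI severity items cover the past 24 hours and current pain, and the first ODI section asks about pain at that moment. If some group 1 participants had been corrected by the physician shortly before the questionnaires, the group 1 versus waiting-list difference would reflect home exercise plus on-demand office care. The dataset would not reliably show who they were.

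**Working it through.** No figure in the plan is in dispute, so the check is a comparison of texts, a count of form items and one proportion.

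**1. Return instructions before month 1, by arm**

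| Arm | Section | Early return offered? |
|---|---|---|
| Group 1 (exercise) | 3.2.2 | Yes, no time limit or stated purpose; all of the arm or accompanied members only |
| Group 2 (belt) | 3.2.3 | Not mentioned |
| Group 3 (waiting list) | 3.2.1 | Not mentioned; fixed appointment at one month |

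Groups 2 and 3 are not barred from contact; their text is silent. Only group 1 has an explicit invitation. If the invitation covers accompanied members only, permitted contact also differs within group 1.

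**2. What a return would contain**

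This is not stated. At the first treatment visit, section 3.2.2 repeats the correction while symptoms and uneven levels persist. Repeat correction at a later return is therefore a reasonable inference, but only an inference.

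**3. Would the data show it?**

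Items listed for the period up to month 1:
- Section 4.2.1: 5 (date; medications, cannabis and alcohol; other treatments; ODI; BPI)
- Section 4.2.2: 4 (side and direction; PSIS distance; post-exercise pain; belt impression)
- Section 4.2.3: 8 (3 for group 1, 4 for group 2, 1 for all)
- Total: 5 + 4 + 8 = 17

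Items naming unscheduled study-clinic contact: 0 of 17. Items open enough to catch it: 1 of 17, the other-treatments entry, which the questionnaire in section 3.3 echoes. Sections 4.1 and 4.2.4 add no such item.

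**4. Size**

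Section 2.2 gives 20 per group. Let k be the number of group 1 participants who return before month 1, and b their mean extra benefit still present at the month-1 questionnaire. Then

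shift in group 1 mean = (k / 20) × b.

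One returner is 1/20 = 5% of the arm. With k = 2 the shift is 2/20 = 10% of b; with k = 5 it is 5/20 = 25% of b. These values of k are illustrations. The documents give neither k nor b, so no shift in ODI or BPI points can be derived. b could be zero, given the statement in section 1.1 that pain recurs with malrotation.

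**The case against.** The strongest reply is that this is leftover practice wording. The surrounding paragraphs read like a description of clinic routine, the section closes with a month at home, and every list of visits contains only scheduled ones. A reader might infer that the two instructions in section 3.2.2 contradict each other. They do not, strictly: sending someone home for a month does not forbid contact with the clinic. If one bullet is for accompanied and the other for unaccompanied members, they address different people. That part of the reply stands.

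It is also fair to say that harm needs three steps, none of them established: someone returns before month 1, the return includes correction, and the benefit lasts to the questionnaire. Participants in all arms come through the same clinic and nothing denies groups 2 and 3 ordinary access. Controls may use manipulation and physical therapy under section 1.1, and the open other-treatments item may catch some returns. As-needed access is also sensible care for a forceful exercise in people aged up to 90. All of this limits the size of the point.

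It does not remove it. Staff and participants act on the text as written, and the text makes the offer to one arm. Outside care is part of the declared control condition and has a form item. Return to the study physician for the assigned exercise is neither, and a participant need not regard it as another treatment.

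**Conclusion.** The point holds as a low-cost improvement. Following section 3.2.2 as written allows extra study-physician contact, offered to group 1 alone, before the month-1 ODI comparison, and no form item is designed to record it. What is at risk is the at-home interpretation of the group 1 result.

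A reader might go further and infer that the group 1 versus waiting-list comparison is invalid. The documents do not support that. The arms are compared as randomised under intention-to-treat (section 5.2), and the contrast remains a valid comparison of what each arm was offered. Nor do the documents show that returns will occur or that they would include correction.

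The size cannot be estimated. Each returner is 5% of the arm, and the shift is k/20 of whatever benefit persists. The effect is probably small. The conclusion rests on two assumptions: that the invitation applies before month 1, since no limit is given, and that some returns would involve supervised correction.

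**What to change.** 1. In section 3.2.2, for months 0 to 1, replace the return clause at the end of the quoted sentence with one contact rule that applies equally to all three arms. Keep contact for side effects and safety open to everyone. State whether any study treatment may be given at such a contact.
2. Add one line to the section 4.2.1 form, for all arms: date, reason and any treatment given at each unscheduled study-clinic contact since the last visit.
3. Report the counts by arm beside the month-1 results, and qualify the home-exercise conclusion if office corrections occurred.

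The cost is half a sentence, one form line and one row in a table. The downside is slightly less physician access for group 1 in the first month or, if returns occur, a narrower claim. Because section 2.2 presents the study as a pilot of the design, the contact counts would also help in planning any later trial.

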3.2.3 Fitting for a pelvic support belt

- A pelvic support belt is a device capable of stabilizing their pelvis^{xvi}, ^{xvii}. The fact that the sacroiliac joint is malrotated indicates a laxity of the ligaments holding this joint in place. This laxity can be the result of old age, a strain, sprain, tear, the presence of relaxin in pregnancy or defective collagen as occurs in Ehlers Danlos syndrome, Marfan's syndrome and hypermobility syndrome. The sacroiliac joint would not be displaced if the ligaments stabilizing it were functioning properly^x. Unless a pelvic belt is worn, particularly during activities where the sacroiliac joints are stressed, there is a very high likelihood of a recurring malrotation. As the goal of this treatment is to provide sufferers with long-term solution for their unstable pelvis, the pelvic belt is a necessary adjunct.

- Participants assigned to group 2 will be fitted for a pelvic support belt and instructed on how to use it: the belt has to be positioned at the level of the sacrum in the back, immediately below the ASISs in front and just above the greater trochanters on the side. It has to be fitted tight, but not excessively^{xvi}, in order to ensure pelvic stability. Preferably it should be worn on top of an undershirt or a crotchless underpant to avoid skin irritation. This being done, they will be sent home for one month with instructions to use the pelvic support belt as needed, whenever they are performing activities which would normally precipitate more back pain.

3.3 Assessment Visit (One Month after the Treatment Visit)

- Participants will answer the questionnaire about the medications, alcohol and marijuana as well as the other therapies they use for pain relief.
- They will be given the BPI NRS pain severity scales and the ODI questionnaire.
- They will once again be assessed, marked, measured and treated: this time participants in all treatment groups will be instructed on how to do the SIFFT and the corresponding corrective exercises. All of them will also receive the pelvic support belt.
- Those in group 1 will report on their use and effectiveness of the corrective exercises. They will then be fitted with a pelvic support belt.
- Those in group 2 will report on their use and the effectiveness of the pelvic support belt. They will then be taught the SIFFT and how to use the exercise corresponding to the direction of their sacroiliac malrotation.
- Those in group 3 will be instructed on how to do the SIFFT and the corresponding corrective exercises. They will also receive the pelvic support belt.
-

3.5 Withdrawal Procedure, Dropouts

- Participants with uneven sacroiliac joints who do not experience any relief after doing the correction exercises and/or trying out the pelvic support belt will probably not want to continue to try these exercises or wear the pelvic support belt at home.
- They will, however, be asked to try the exercise and belt at home and return in 1 month to be retested and fill out the questionnaires. At that time, all the procedures associated with the first treatment visit will be repeated.
- For those who decide to withdraw from the study, every effort will be made to contact them and ask them the questionnaire relevant to the time they withdrew,
- unless, at the time they withdraw they notify us that they do not want to answer any more questionnaires, in which case the last data collected will be entered in the database.

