5.0 Statistics

5.1 Outcome Measures

5.1.1A Primary Outcomes For the First Study

- difference in the change in ODI score in the initial treatment visit questionnaire and at the assessment visit one month later in the control group compared to the change from the treatment visit questionnaire to the 1 month assessment follow-up visit in the immediate SIFFT and exercise treatment group.
- difference in the change in ODI score in the treatment visit questionnaire and at the assessment visit, one month later, in the control group compared to the change from the treatment visit questionnaire to the 1 month assessment follow-up visit in the immediate pelvic support belt treatment group.

5.1.2A Secondary Outcomes For the First Study

- difference in the change in BPI NRS pain severity scores in the treatment visit questionnaire and at the assessment visit, one month later, in the control group compared to the change from the treatment visit questionnaire to the 1 month follow-up assessment visit in the immediate SIFFT and exercise treatment group.
- difference in the change in BPI NRS pain severity scores in the treatment visit questionnaire and at the assessment visit, one month later, in the control group compared to the change from the treatment visit questionnaire to the 1 month follow-up assessment visit in the immediate pelvic support belt treatment group.

5.1.1B Primary Outcome For the Follow-up Study

- difference in the change in ODI score in the assessment visit questionnaire and at the reassessment visit, two months later, for all groups.

5.1.2B Secondary Outcome For the Follow-up Study

- difference in the change in BPI NRS pain severity scores in the assessment visit questionnaire and at the reassessment visit, two months later, for all groups.

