5.2 Statistical Analysis

Data will be analyzed using PASW Statistics 18, Release 18.0.0, IBM. Analysis will be performed by intention-to-treat. Descriptive statistics (mean value \pm standard deviation (SD)) will be calculated for outcome variables at each time point. Baseline between-group data will be analyzed for significant differences by t-tests for nominal variables and Pearson chi square tests for categorical variables. Baseline characteristics will be included in the model as covariates for those variables with a significant between group difference. Analyses of covariates will be applied to compare the groups for magnitude of change in the 0-10 NRS pain score and Oswestry Disability Index between baseline and each follow-up time point (0, 1 and 2 months). A two-tailed P value $<.05$ will be used as the statistical significance level.

- a Pearson's chi-square-test will be done to assess the significance of the difference in Oswestry low back disability score over a 1 month period between

those who are treated with the immediate SIFFT and exercise treatment group, the immediate pelvic support belt group and those who are in the observation group.

- A second Pearson's chi-square will be done to assess the significance of the difference in BPI NRS pain severity score over a 1 month period between those who are treated with the immediate SIFFT and exercise treatment group, the immediate pelvic support belt group and those who are in the observation group.
- A student t-test will be done to assess the significance of the difference in ODI score over a one month period when both treatments are used simultaneously.
- A student t-test will be done to assess the significance of the difference in BPI NRS pain severity score over a one month period when both treatments are used simultaneously.
- The average and standard deviation for all the other data will be calculated and reported on.

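### Section 3.5 makes no provision for collecting the scheduled month 1 and month 2 ODI and BPI from participants who withdraw but are still willing to answer

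*Combined protocol and SAP*

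**What the plan says.** Section 3.5 deals with three kinds of participant.

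- **No relief, still in the study.** The section expects that they "will probably not want to continue to try these exercises or wear the pelvic support belt at home", but they are asked to try the treatment at home and "return in 1 month to be retested and fill out the questionnaires".
- **Withdrawn, and has not refused questionnaires.** For these, "every effort will be made to contact them and ask them the questionnaire relevant to the time they withdrew".
- **Withdrawn, and has told the study that** "they do not want to answer any more questionnaires, in which case the last data collected will be entered in the database".

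Section 3.5.1 separately carries the last value forward to each missed visit for participants lost to follow-up.

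Section 5.1.1A defines the primary outcomes of the first study as the ODI change from the treatment visit to one month. Each treated group is compared with the change measured "at the assessment visit one month later in the control group". Section 5.1.1B takes the ODI change from the assessment visit to the reassessment visit, in all groups, as the primary outcome of the follow-up study. Section 5.2 states: "Analysis will be performed by intention-to-treat".

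In the first month the control condition is a "waiting list for one month, using usual treatments such as medications" and other usual care. At the one-month visit every group is taught the exercise, and "All of them will also receive the pelvic support belt" (section 3.3).

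**The concern.** An intention-to-treat analysis of change between fixed visits needs the scheduled score from everyone willing to give it, whether or not they still use the exercise or belt. For willing withdrawers, section 3.5 ties collection to the time of withdrawal and sets no later contact.

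Timing matters because the instruments measure current state. ODI section 1 asks about pain at the moment. The BPI worst and least items cover the last 24 hours, and another item asks about pain right now. An answer given a week after treatment starts is not a one-month answer.

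The loss may also be uneven at the primary comparison. Lack of relief is the reason for not continuing that section 3.5 itself expects. Before month 1, lack of relief from study treatment can arise only in groups 1 and 2, because group 3 is still waiting.

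The lists in section 4 contain no item for the reason for withdrawal. Side effects are asked only in the month 1 and month 2 lists (sections 4.2.3 and 4.2.4), so a participant who leaves because of one may not have it recorded.

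**Working it through.** **1. Reading the rule against the outcomes.** Section 3.5 does not say when the questionnaire is to be completed, so two readings are open.

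| | Reading A: form answered at the withdrawal contact | Reading B: form belonging to that period |
|---|---|---|
| Withdraws in month 1: month 1 ODI | Mistimed | Sought, but no completion date stated |
| Withdraws in month 1: month 2 ODI | No stated collection | No stated collection |
| Withdraws in month 2: month 2 ODI | Mistimed | Sought, but no completion date stated |

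Reading A affects the primary outcomes of both studies. Reading B can preserve the month 1 outcome but leaves the follow-up study without a month 2 score for anyone who withdrew in month 1.

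**2. Stated figures.** Section 2.2 gives 20 per group and 60 overall: 3 × 20 = 60, reproduced. The plan states no SD, power or withdrawal rate, so everything below rests on assumptions.

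**3. Shift in an arm mean from mistimed scores.** Inputs: n = 20 per arm (section 2.2), so one withdrawer is 1/20 = 5% of an arm. Assumed: 1 to 4 withdrawers (5% to 20%), and 5 to 10 ODI points between the withdrawal score and the scheduled score.

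Shift = withdrawing fraction × score difference

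- Low end: 0.05 × 5 = 0.25 points
- High end: 0.20 × 10 = 2.0 points

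If the 10% in section 1.2 is read as 10 ODI points (an assumption), the high end is 2.0/10 = one fifth of the target. The shift passes in full to the between-group contrast only if the other arm has none. Its sign depends on whether scores rise or fall after withdrawal, which the documents do not show.

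**4. Comparison with sampling error.** With an assumed SD of change of 15, the standard error of a between-group difference is 15 × √(2/20) = 4.7 points. The shift is therefore about 0.25/4.7 = 0.05 to 2.0/4.7 = 0.4 standard errors.

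**5. If the scores are missing rather than mistimed.** Two-sided alpha is 0.05 (section 5.2). The assumed difference is 10 points and the assumed SD is 12, 15 or 18. Using the normal approximation, with n_t the number of treated participants with a month 1 score:

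Power = Φ(10 / (SD × √(1/20 + 1/n_t)) − 1.96)

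| SD | n_t = 20 | n_t = 18 (10% lost) | n_t = 16 (20% lost) |
|---|---|---|---|
| 12 | 75% | 73% | 70% |
| 15 | 56% | 54% | 51% |
| 18 | 42% | 40% | 38% |

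The loss is about 2 to 5 percentage points.

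**6. If a baseline value were entered for month 1.** The document states carry-forward to missed visits for participants lost to follow-up, not for willing withdrawers, so this is a side calculation. The shift in the estimated difference is −w × d, where w is the treated-arm withdrawing fraction and d the withdrawers' true month 1 improvement. At w = 20%:

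- d = −5: +1.0 point
- d = 10: −2.0 points
- d = 15: −3.0 points

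At w = 5%, the same range of d gives +0.25 to −0.75.

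**The case against.** The strongest reply is that section 3.5 already does much of what is asked. It requests that participants without relief return at 1 month and complete the questionnaires. A reader might infer that stopping the exercise or belt ends outcome collection. The text does not support that: only formal withdrawal brings the rule at issue into play. This part of the reply stands.

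Second, the study has different question lists by period, so the form relevant to the time of withdrawal may well be the month 1 form. The refusal clause speaks of questionnaires in the plural, which suggests that later contact is possible. A reader might infer that withdrawers get one questionnaire and no more, repeat the baseline form, or have a week 1 score entered as month 1. None of these is stated. The wording is ambiguous and does not prohibit later collection. But the plural describes what may be refused and schedules nothing, and the period-form reading still leaves month 2 without stated collection for a month 1 withdrawer.

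Third, if the month 1 form is used, it asks side effects of the exercise in group 1 and of the belt in group 2. Section 4.2.1 also already records the date of each scheduled questionnaire. So under-counting of side effects is a possibility and not a consequence of the text. The absence of a recorded reason for withdrawal remains.

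Fourth, the shift is small beside the sampling error of a 20-per-group pilot, and its inputs are assumed. That is correct and limits the weight of the point. The remedy is cheap enough to be worthwhile all the same.

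**Conclusion.** The concern holds in limited form. For formal withdrawers who have not refused further questionnaires, the document does not provide for ODI and BPI at the scheduled month 1 and month 2 dates, and this does not fit an intention-to-treat analysis of visit-based change. On one reading the month 1 ODI is mistimed. On both, a month 1 withdrawer has no stated month 2 collection. Two readings of one rule also allow similar participants to be handled differently.

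A reader might conclude that the lost data fall mainly in the treated groups. The documents support only something narrower: withdrawal for lack of relief from study treatment cannot arise in group 3 during month 1. No withdrawal rates are given, controls may leave for other reasons, and in month 2 all groups are treated.

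The illustrated size is 0.25 to 2.0 ODI points on an arm mean, or about 2 to 5 percentage points of power if scores are simply missing. The first figure assumes 5% to 20% withdrawal and a 5 to 10 point score difference. The second assumes 10% to 20% loss in the treated arm, a 10-point effect and SDs of 12 to 18. The direction of the shift is unknown. This is a cheap improvement that should be made, not a flaw that invalidates the design.

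**What to change.** Amend section 3.5 as follows.

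- Ask every withdrawer who has not refused further contact to complete the ODI and BPI at the scheduled one-month and two-month dates, by telephone, mail or email, whatever treatment they are then using.
- Record the actual completion date and the mode of completion.
- Do not use a score taken at the withdrawal contact as the month 1 or month 2 value when the scheduled score can be obtained.
- At the withdrawal contact, record the reason for withdrawal and any side effects.

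The cost is a few sentences and a small number of contacts by the office assistant. The ODI and BPI are self-report, and section 3.1 already has the office sending a questionnaire by mail or email. The downside is that a few participants will complete the forms remotely, which should be flagged in the data.
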